5.2.2. Additional considerations

- The analysis of demographic characteristics by group will be performed on the ES and on the PPS.
- Demography and baseline characteristics will also be summarized by sex and region.
- A summary of important protocol deviations leading to elimination from any analyses will be provided by group, based on the Enrolled Set.
- Medical history will be tabulated by System Organ Class (SOC), High Level Term (HLT) and Preferred Term (PT).

5.3. Primary endpoint(s)

5.3.1. Analysis planned in the protocol

The primary analysis for immunogenicity will be performed on the PPS. If the percentage of vaccinated participants with serological results excluded from the PPS for immunogenicity is at least 5% for at least 1 visit and at least 1 group, a second analysis will be performed on the ES.

5.3.1.1. Humoral immune response – up to Month 12

The analysis of the primary vaccination timepoints up to Month 12 will be performed for each group and for the 3 groups pooled. For each timepoint with blood sample collection for humoral immune response up to Month 12 and for each assay (RSV-A/-B neutralization assays), unless otherwise specified, the following analyses will be performed:

Within groups evaluation:

- Percentage of participants with antibody titers/concentrations above or equal to the technical assay cut-off and their exact 95% confidence interval (CI) will be tabulated.
- GMTs/GMCs and their 95% CI will be tabulated and represented graphically. Furthermore, to account for all the timepoints at which the blood samples are collected, a mixed effects model (see Section 5.4.3.1) will be fitted, from which the GMTs/GMCs will be computed.
- Antibody titers/concentrations will be displayed using reverse cumulative curves.
- The MGI i.e. geometric mean of ratios of antibody titer/concentrations will be tabulated with 95% CI.

5.4. Secondary endpoint(s)

5.4.1. Humoral immune response

The same analyses as described above for the primary endpoint will be performed for RSVPreF3-specific IgG ELISA up to Month 12 and for each timepoint with blood sample collection for humoral immune response **from study Month 13 up to study end** and for each assay (RSVpreF3-specific IgG **ELISA and RSV-A/-B neutralization assays**). For Month 13, Month 18, and Month 24, the analyses will be tabulated for RSV_annual group versus the pooled RSV_flexible revaccination and RSV_1dose groups. From Month 25 up to study end, the analyses will be performed by group.

Only the analyses requiring further clarification of the exact timepoints analyzed are summarized below:

Within groups evaluation:

- The MGI i.e. geometric mean of ratios of antibody titer/concentrations will be tabulated with 95% CI:
 - For each post-primary vaccination time point (at Months 18, 24, 30 and 36 when applicable) over pre-primary vaccination (Day 1),
 - For each post-revaccination time point over corresponding pre-revaccination (Months 12 and 24) in the RSV_annual group,
 - For each post-revaccination timepoint over corresponding pre-revaccination (Month 24) in the RSV_flexible revaccination group,
 - For 1 month post-revaccination at Month 12 (Month 13) over 1 month post-Dose 1 vaccination (Day 31) in RSV_annual group.
 - For 1 month post-revaccination at Month 24 (Month 25) over 1 month post-revaccination at Month 12 (Month 13) in RSV_annual group
 - For 1 month post-revaccination at Month 24 (Month 25) over 1 month post-Dose 1 vaccination (Day 31) in RSV_flexible revaccination group.

In addition, the following evaluation will be performed:

• The kinetics of GMTs/GMCs will be plotted as a function of time for participants with results available at all post vaccination timepoints.

The immunogenicity analysis will be performed overall, by sex, age category (age at Dose $1: \ge 65$ YOA, ≥ 70 YOA, ≥ 80 YOA, 60-69 YOA and 70-79 YOA), and region (North America, Europe, Asia).

5.4.2. Cell-mediated immune response

Within groups evaluation:

The following parameters will be summarized by group at each timepoint for which blood samples are collected, for the 3 groups pooled for time points up to study Month 12, for Month 13, Month 18 and Month 24, the analyses will be tabulated for RSV_annual group versus the pooled RSV_flexible revaccination and RSV_1dose groups. From Month 25 up to study end, the analyses will be performed by group using descriptive statistics (N, geometric mean, min, Q1, median, Q3, max) in the CMI subset:

- Frequency of RSVPreF3-specific CD4+ and/or CD8+ T cells expressing at least 2 activation markers including at least one cytokine among CD40L, 41BB, IL-2, TNF-α, IFN-γ, IL-13, IL-17, measured by intracellular cytokine staining (ICS) using peripheral blood mononuclear cells PBMCs.
- The kinetics of RSVPreF3-specific CD4+ T cells frequencies will be plotted as a function of time for participants with results available at all timepoints.
- Fold increase of the frequency of RSVPreF3-specific CD4+ T cells expressing at least 2 activation markers including at least one cytokine among CD40L, 41BB, IL-2, TNF-α, IFN-γ, IL-13, IL-17, measured by ICS at each post-primary vaccination timepoint over pre-vaccination (Day 1) by group, at each post-

revaccination over the corresponding pre-revaccination (Month 12/Month 24 in the RSV_annual group and Month 24 in the RSV_flexible revaccination group), at one month post-revaccination over 1 month post-previous dose in the RSV_annual group [one month post-revaccination at Month 12 (Month 13) over one month post-Dose 1 vaccination (Day 31) and one month post-revaccination at Month 12 (Month 13)] and in the RSV_flexible revaccination group [one month post-revaccination at Month 12 (Month 13)] and in the RSV_flexible revaccination group [one month post-revaccination at Month 12 (Month 13)] and in the RSV_flexible revaccination group [one month post-revaccination at Month 12 (Month 13)] and in the RSV_flexible revaccination group [one month post-revaccination at Month 24 (Month 25) over one month post-revaccination at Month 12 (Month 13)] and in the RSV_flexible revaccination group [one month post-revaccination at Month 24 (Month 25) over one month post-Dose 1 vaccination (Day 31)].

The immunogenicity analysis will be performed overall, by sex, age category (age at Dose $1: \ge 65$ YOA, ≥ 70 YOA, ≥ 80 YOA, 60-69 YOA and 70-79 YOA, and region (North America, Europe, Asia).

5.4.3. Additional considerations

5.4.3.1. Mixed effects model

For the GMTs/GMCs calculation based on the mixed effects model mentioned in Section 5.3.1.1, repeated measures analysis of covariance (ANCOVA) model will be fitted including age category (60-69 YOA, 70-79 YOA and \geq 80 YOA,), study group (RSV_annual, RSV_flexible revaccination and RSV_1dose), sex (male and female), visit (Day 31, Months 6, 12, 13, 18, 24, 25, 30, 36), as fixed effects, pre-vaccination log10-transformed titers/concentrations as a covariate and the response variable is the post-vaccination log10-transformed titers/concentrations. The PROC MIXED procedure in SAS® will be used to carry out the ANCOVA.

The following SAS codes will be used:

For the analysis by study group, study group and visit will be included as the fixed effects in the model

```
Analysis by group
PROC MIXED DATA=SERO method=reml empirical;
CLASS subjid group visit ;
MODEL post-vac=pre-vacc group visit visit*group/ noint s cl;
RANDOM intercept/ subject=usubjid g v vcorr type = un;
REPEATED visit/type=unsubject=subjid;
LSMEANS visit*group/ E cl;
ODS OUTPUT LSMEANS=LS;
RUN;
```

For the analysis by age category, age category and visit will be included as the fixed effects in the model. However, this is only applicable at timepoints where the 3 study groups will be pooled. Otherwise for the timepoints where pooling of the 3 groups is not possible, the fixed effects will include study group, age category and visit.

Analysis by age-category

```
PROC MIXED DATA=SERO method=reml empirical ;
CLASS subjid visit agecat ;
MODEL post-vac=pre-vacc agecat visit visit* agecat /noint s cl;
RANDOM intercept/ subject=subjid g v vcorr type = un;
REPEATED visit/type=un subject=subjid;
LSMEANS visit*agecat/ E cl;
ODS OUTPUT LSMEANS=LS;
RUN;
```

For the analysis by sex, sex and visit will be included as the fixed effects in the model. However, this is only applicable at timepoints where the 3 study groups will be pooled. Otherwise for the timepoints where pooling of the 3 groups is not possible, the fixed effects will include study group, sex and visit.

Analysis by sex

```
PROC MIXED DATA=SERO method=reml empirical;
CLASS subjid visit agecat ;
MODEL post-vac=pre-vacc sex visit visit* sex / noint s cl;
RANDOM intercept/ subject=usubjid g v vcorr type = un;
REPEATED visit/type=un subject=subjid;
LSMEANS visit*sex/ E cl;
ODS OUTPUT LSMEANS=LS;
RUN;
```

For the analysis by region, region and visit will be included as the fixed effects in the model. However this is only applicable at timepoints where the 3 study groups will be pooled. Otherwise for the timepoints where pooling of the 3 groups is not possible, the fixed effects will include study group, region and visit.

```
Analysis by region
```

```
PROC MIXED DATA=SERO method=reml empirical;
CLASS subjid visitregion ;
MODEL post-vac=pre-vacc region visit visit* region / noint scl;
RANDOM intercept/ subject=usubjid g v vcorr type = un;
REPEATED visit/type=un subject=subjid;
LSMEANS visit*region/ E cl;
ODS OUTPUT LSMEANS=LS;
RUN;
```

The GMTs/GMCs, lower and upper confidence limits are obtained from the following data step:

```
DATA LS;
   SET LS;
   gm=10**estimate;
   ll=10**lower;
   ul=10**upper;
RUN;
```

The above SAS codes may be adapted in case of convergence issues.

5.4.3.2. Cell-mediated immune response

Within groups evaluation

- The frequency of RSVPreF3 specific-CD4+ T cells will be displayed graphically using boxplots (min, Q1, median, Q3, max), by group and timepoint.
- The RSVPreF3-specific CD4+/ CD8+ T cell frequencies will be obtained by subtracting the background value to the antigen-induced value, and by setting to 1 all values less than or equal to zero for geomean calculation and graphical representation. Frequencies will be expressed as the number of cells per million of CD4+ T cells.
- More specifically, the frequencies of RSVPreF3-specific CD4+/ CD8+ T cells expressing at least 2 activation markers including at least one cytokine [*Freq*²⁺] will be computed as follows:

$$Freq_{Background}^{2+} = \frac{n_{background}^{2+}}{N_{Background}^{CD4}} \quad \text{and} \quad Freq_{Induction}^{2+} = \frac{n_{Induction}^{2+}}{N_{Induction}^{CD4}},$$

And

$$Freq_{Specific}^{2+} = Freq_{Induction}^{2+} - Freq_{Background}^{2+}$$

where

 $n_{Background}^{2+}$ = number of CD4+ T cells expressing at least 2 activation markers including at least one cytokine after stimulation with medium only (background),

 $n_{Induction}^{2+}$ = number of CD4+ T cells expressing at least 2 activation markers including at least one cytokine after stimulation with a pool of peptides covering RSVPreF3 (induction),

 $N_{Back/Ind}^{CD4}$ = Total number of CD4 T cells involved in the assay (background or induction).

For the computation of the fold increase (post- over pre-vaccination) of the frequency of RSVPreF3-specific CD4+ T-cells identified as expressing **at least 2 activation marker(s) including at least one cytokine** among CD40L, 4-1BB, IL-2, TNF- α , IFN- γ , IL-13, IL-17.the results **below the LLOQ** of the assay will be replaced by the value of the LLOQ.

5.4.3.3. Assessment of long-term persistence of the immune response at Months 18, 24 and 36 after dose 1

The exploratory analysis for modelling the long-term persistence of immune response (humoral and cellular) post dose 1 vaccination will constitute of the following;

- A piece-wise linear mixed model, power law model and modified power law model [David et al, 2009] for repeated measurements (all data available from Day 1, 31 and Month 6, 12, 18, 24, 30, 36 post-Dose 1 vaccination, will be used to model over time
 - the frequency of RSVPreF3-specific CD4+ T cells expressing at least 2 activation markers including at least one cytokine among CD40L, 4-1BB, IL-2, TNF-α, IFN-γ, IL-13, IL-17.
 - the neutralizing antibody titers against RSV-A, RSV-B and RSVPreF3-specific IgG antibody concentrations.

The *piece-wise linear mixed model* is expressed as follows

The piece-wise model fits the data on three non-overlapping time intervals. This corresponds to the observed decay of humoral and cellular antibodies. Each piece of the model uses a linear function. Three break points, Months x, xx and xxx, will be selected on the basis of Akaike's Information Criterion (AIC) [Pan, 2001].

$$(ft) = \beta_0 + \beta_1 t \quad \text{if } x \le t < xx \text{ months}$$
$$(ft) = \beta_0 + \beta_1 t + \beta_2 (t - xx) \quad \text{if } xx \le t < xxx \text{ months.}$$
$$(ft) = \beta_0 + \beta_1 t + \beta_2 (t - xx) + \beta_3 (t - xxx) \quad \text{if } t \ge xxx \text{ months}$$

where f(t) is the log-10 transformed antibody titer/concentration/ RSVPreF3-specific CD4+ T cells at time t post-vaccination, β_0 is the intercept and $\beta_1(i = 1,2,3)$ are the parameters corresponding to the three time intervals, respectively. All three model effects

Statistical Analysis Plan Amendment 2

will be fitted using the SAS PROC MIXED standard code for linear regression methodology

```
ODS OUTPUT FitStatistics= stat;
ODS OUTPUT ConvergenceStatus= conv;
PROC MIXED DATA=kin&i.&j. EMPIRICAL COVTEST NOCLPRINT IC;
CLASS pid;
MODEL log_val = int_m int_m_pw_m&i.*m&i. int_m_pw_m&j.*m&j./s cl
covb outp=pred outpm=predm;
RANDOM intercept/SUBJECT=pid;
MAKE "solutionF" out=est;
RUN;
```

The *power-law model* is expressed as follows:

 $f(t) = k - a \log(c + t)$

where f(t) is the log-10 transformed antibody titer/concentration/ RSVPreF3-specific CD4+ T cells at time t post-vaccination, k is the peak log level, a is the decay rate, and c is an arbitrary small constant (set to zero in this case). The estimated maximum likelihood (ML) values for the model parameters will be obtained using the PROC NLMIXED SAS procedure.

```
PROC NLMIXED DATA=kineticm;
PARMS se=&se a0 =&a k0 =&k sk=&sk sa=&sa ska=&ska;
q = (1/&time)**a;
lg=&log(q);
mean = k + lg;
MODEL log_val ~ NORMAL(mean,se*se);
RANDOM k a ~ NORMAL([k0,a0], [sk*sk, ska, sa*sa]) SUBJECT=pid out=indiv;
RUN;
```

The *modified power-law model* is expressed as follows:

It is an extension of the power law model, and it is expressed as follows.

 $f(t) = k + \log[(1 - \pi)(c + t)^a + \pi]$

The quantity π (between 0 and 1) represents the proportion of antibodies that are produced in the long term. When the value of π is positive, this implies long-term antibody persistence, as noted by [Fraser et al, 2007]. If $\pi = 0$, then the modified power-law model reduces to the standard power-law model. The estimated maximum likelihood (ML) values for the model parameters will be obtained using the PROC NLMIXED SAS procedure.

```
PROC NLMIXED DATA=kineticm ;
PARMS pi=&pi se=&se a0 =&a k0 =&k sk=&sk sa=&sa ska=&ska;
q = (1-pi)*(1/&time)**a;
lg=&log(q+pi);
mean = k + lg;
MODEL log_val ~ NORMAL(mean,se*se);
RANDOM k a ~ NORMAL([k0,a0], [sk*sk, ska, sa*sa]) SUBJECT=pid out =indiv
RUN;
```

- The three models based on data up to Month 36 will be presented graphically. Models based on data up to Month 18 vs. Month 24, Month 24 vs. Month 30 and Month 30 vs. Month 36 will be presented side by side.
- The above models and SAS codes may be adapted in case of convergence issues.

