9.2. Sample size determination (Amended: 01 April 2022)

This study is planned to enroll ~1650 participants randomized according to 3:1:1 ratio to 1 of the 3 study groups: RSV_annual, RSV_flexible revaccination, and RSV_1dose respectively.

The proposed sample size is based on the following considerations:

• Ensure a sufficient number of participants to evaluate with adequate precision the immunogenicity after a single dose regimen up to 12 months post-vaccination (based on the 3 pooled RSV_annual, RSV_flexible revaccination and RSV_ldose groups) but also the immunogenicity after revaccination (based on RSV_annual and RSV_flexible revaccination groups).

- Ensure adequate description of the antibody kinetics after a single dose keeping the flexibility to give a revaccination to a part of the participants.
- Ensure an adequate sample size for evaluation of reactogenicity and safety profile following revaccination.

Approximately 345 participants will be enrolled in the humoral subset in the RSV_annual group and approximately 330 participants per group in the RSV_flexible revaccination and RSV_1dose groups. Approximately 345, 115 and 115 participants will be enrolled in the CMI subset in the RSV_annual, RSV_flexible revaccination, and RSV_1dose groups, respectively. A total of 990 and 330 participants will be enrolled in the RSV_annual and RSV_flexible revaccination groups, respectively, for evaluation of reactogenicity and safety profile following revaccination. A 20% rate of non-evaluable participants every year will be considered.

Withdrawals will not be replaced.

9.2.1. Evaluation of humoral immune response up to Month 12 (primary objective and first secondary objective)

At Month 12, the effect of a 1-dose primary schedule will be evaluated in terms of RSV-A/B neutralizing antibody titers and RSVPreF3-specific IgG concentrations. Approximately 804 participants in the (RSV_annual, RSV_flexible revaccination, and RSV_1dose) pooled group receiving a single dose of RSVPreF3 OA investigational vaccine will be evaluable for the humoral immune response at Month 12.

Table 17 shows the precision that can be obtained based on different values of standard deviations in terms of RSV-A/B neutralizing antibody titers, and RSVPreF3-specific IgG antibody concentrations.

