5.1.2. Immunogenicity

- Any missing or non-evaluable immunogenicity measurement will not be replaced. The descriptive analysis performed for each assay at each timepoint will exclude participants with a missing or non-evaluable measurement. This is applicable to the standard way of computing geometric mean titers/concentrations (GMTs/GMCs).
- During the computation of GMTs/GMCs from the mixed effects model (Section 5.4.3.1). Multiple imputation (MI) technique will not be applied for any missing immunogenicity measurement. This is because the mixed effects model inherently accounts for the missingness, under the assumption that the missing data are missing at random (MAR). Thus considering that missing data are MAR is a reasonable assumption for this descriptive clinical trial, then it is not necessary to perform MI [Rubin et al., 1995]
- The GMTs/GMCs will be computed by taking the anti-logarithm of the arithmetic mean of the log₁₀ transformed titers/concentrations.
- A seronegative participant will be defined as a participant whose antibody titer/concentration is below the technical cut-off value of the assay. A seropositive participant is a participant whose antibody titer/concentration is greater than or equal to the technical cut-off value of the assay.
- Antibody titers/concentrations below the technical assay cut-off will be given an arbitrary value of half the technical assay cut-off for the purpose of GMT/GMC calculation.
- Antibody titers/concentrations above the Upper Limit of Quantification (ULOQ) value will be given the ULOQ value for the purpose of GMT/GMC calculation.
- The mean geometric increase (MGI) is calculated by the geometric mean of ratios of antibody titers/concentrations of each post vaccination time point over pre vaccination (Day 1).

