5.4.3.2. Cell-mediated immune response

Within groups evaluation

- The frequency of RSVPreF3 specific-CD4+ T cells will be displayed graphically using boxplots (min, Q1, median, Q3, max), by group and timepoint.
- The RSVPreF3-specific CD4+/ CD8+ T cell frequencies will be obtained by subtracting the background value to the antigen-induced value, and by setting to 1 all values less than or equal to zero for geomean calculation and graphical representation. Frequencies will be expressed as the number of cells per million of CD4+ T cells.
- More specifically, the frequencies of RSVPreF3-specific CD4+/ CD8+ T cells expressing at least 2 activation markers including at least one cytokine [*Freq*²⁺] will be computed as follows:

$$Freq_{Background}^{2+} = \frac{n_{background}^{2+}}{N_{Background}^{CD4}} \quad \text{and} \quad Freq_{Induction}^{2+} = \frac{n_{Induction}^{2+}}{N_{Induction}^{CD4}},$$

And

$$Freq_{Specific}^{2+} = Freq_{Induction}^{2+} - Freq_{Background}^{2+}$$

where

 $n_{Background}^{2+}$ = number of CD4+ T cells expressing at least 2 activation markers including at least one cytokine after stimulation with medium only (background),

 $n_{Induction}^{2+}$ = number of CD4+ T cells expressing at least 2 activation markers including at least one cytokine after stimulation with a pool of peptides covering RSVPreF3 (induction),

 $N_{Back/Ind}^{CD4}$ = Total number of CD4 T cells involved in the assay (background or induction).

For the computation of the fold increase (post- over pre-vaccination) of the frequency of RSVPreF3-specific CD4+ T-cells identified as expressing **at least 2 activation marker(s) including at least one cytokine*** among CD40L, 4-1BB, IL-2, TNF- α , IFN- γ , IL-13, IL-17.the results below the LLOQ of the assay will be replaced by the value of the LLOQ.

* cytokines are IL-2, TNF-α, IFN-γ, IL-13, and IL-17

5.4.3.3. Assessment of long-term persistence of the immune response at Months 18, 24 and 36 after dose 1

The exploratory analysis for modelling the long-term persistence of immune response (humoral and cellular) post dose 1 vaccination will constitute of the following;

- A piece-wise linear mixed model, power law model and modified power law model [David et al, 2009] for repeated measurements (all data available from Day 31, Month 6, 12, 18, 24, 30, 36 post-Dose 1 vaccination, will be used to model over time

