 - the frequency of RSVPreF3-specific CD4+ T cells expressing at least 2 activation markers including at least one cytokine among CD40L, 4-1BB, IL-2, TNF-α, IFN-γ, IL-13, IL-17.
 - the neutralizing antibody titers against RSV-A, RSV-B and RSVPreF3-specific IgG antibody concentrations.

The *piece-wise linear mixed model* is expressed as follows

The piece-wise model fits the data on non-overlapping time intervals. This corresponds to the observed decay of humoral and cellular antibodies. Each piece of the model uses a linear function. Break points will be selected on the basis of Akaike's Information Criterion (AIC) [Pan, 2001].

$$(ft) = \beta_0 + \beta_1 t \quad \text{if } x \le t < xx \text{ months}$$
$$(ft) = \beta_0 + \beta_1 t + \beta_2 (t - xx) \quad \text{if } xx \le t < xxx \text{ months}.$$
$$(ft) = \beta_0 + \beta_1 t + \beta_2 (t - xx) + \beta_3 (t - xxx) \quad \text{if } t \ge xxx \text{ months}$$

where f(t) is the log-10 transformed antibody titer/concentration/ RSVPreF3-specific CD4+ T cells at time t post-vaccination, β_0 is the intercept and $\beta_1(i = 1,2,3...)$ are the

Statistical Analysis Plan Amendment 3

parameters corresponding to the time intervals, respectively. All the model effects will be fitted using the SAS PROC MIXED standard code for linear regression methodology for repeated data.

```
ODS OUTPUT FitStatistics= stat;
ODS OUTPUT ConvergenceStatus= conv;
PROC MIXED DATA=kin&i.&j. EMPIRICAL COVTEST NOCLPRINT IC;
CLASS pid;
MODEL log_val = int_m int_m_pw_m&i.*m&i. int_m_pw_m&j.*m&j./s cl
covb outp=pred outpm=predm;
RANDOM intercept/SUBJECT=pid;
MAKE "solutionF" out=est;
RUN;
```

The *power-law model* is expressed as follows:

 $f(t) = k - a \log(c + t)$

where f(t) is the log-10 transformed antibody titer/concentration/ RSVPreF3-specific CD4+ T cells at time t post-vaccination, k is the peak log level, a is the decay rate, and c is an arbitrary small constant (set to zero in this case). The estimated maximum likelihood (ML) values for the model parameters will be obtained using the PROC NLMIXED SAS procedure.

```
PROC NLMIXED DATA=kineticm;
PARMS se=&se a0 =&a k0 =&k sk=&sk sa=&sa ska=&ska;
q = (1/&time)**a;
lg=&log(q);
mean = k + lg;
MODEL log_val ~ NORMAL(mean,se*se);
RANDOM k a ~ NORMAL([k0,a0], [sk*sk, ska, sa*sa]) SUBJECT=pid out=indiv;
RUN;
```

The *modified power-law model* is expressed as follows:

It is an extension of the power law model, and it is expressed as follows.

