 $f(t) = k + \log[(1 - \pi)(c + t)^a + \pi]$

The quantity π (between 0 and 1) represents the proportion of antibodies that are produced in the long term. When the value of π is positive, this implies long-term antibody persistence, as noted by [Fraser et al, 2007]. If $\pi = 0$, then the modified power-law model reduces to the standard power-law model. The estimated maximum likelihood (ML) values for the model parameters will be obtained using the PROC NLMIXED SAS procedure.

```
PROC NLMIXED DATA=kineticm ;
PARMS pi=&pi se=&se a0 =&a k0 =&k sk=&sk sa=&sa ska=&ska;
q = (1-pi)*(1/&time)**a;
lg=&log(q+pi);
mean = k + lg;
MODEL log_val ~ NORMAL(mean,se*se);
RANDOM k a ~ NORMAL([k0,a0], [sk*sk, ska, sa*sa]) SUBJECT=pid out =indiv
RUN;
```

- The three models based on data up to Month 36 will be presented graphically. Models based on data up to Month 18 vs. Month 24, Month 24 vs. Month 30 and Month 30 vs. Month 36 will be presented side by side.
- The above models and SAS codes may be adapted in case of convergence issues.

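### The piece-wise persistence model allows no person-to-person variation in decay, so its late means are biased, in either direction, if decay varies and loss depends on earlier titre

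*SAP*

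**What the plan says.** SAP Amendment 3, section 5.4.3.3, models persistence after Dose 1 in three ways, using "all data available from Day 31, Month 6, 12, 18, 24, 30, 36 post-Dose 1 vaccination". The section calls the analysis exploratory and plans to plot all three models.

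- **Piece-wise linear model.** The call is "PROC MIXED DATA=kin&i.&j. EMPIRICAL COVTEST NOCLPRINT IC" and the only random-effects statement is "RANDOM intercept/SUBJECT=pid". There is no random slope and no REPEATED statement. Break points are chosen by AIC. Amendment 2 has the same RANDOM line.
- **Power-law model.** "RANDOM k a ~ NORMAL([k0,a0], [sk*sk, ska, sa*sa]) SUBJECT=pid out=indiv": level k and decay a both vary between people, with a covariance.
- **Modified power-law model.** The same two correlated random effects.

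The GMT model in section 5.4.3.1 uses an unstructured covariance over visits. For that model, section 5.1.2 relies on data being missing at random. Section 5.4.3.3 states no missing-data assumption of its own.

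Protocol 9.2 states: "A 20% rate of non-evaluable participants every year will be considered". It adds: "Withdrawals will not be replaced".

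**The concern.** The piece-wise model is the only longitudinal model in the SAP that rules out individual decay, and no reason is given. A likelihood-based mixed model is protected against loss at random only if its covariance is adequate. With an intercept alone, a leaver's later course is filled in by carrying a constant offset from the average curve. If decay truly varies, a leaver's last titres also carry information about that person's slope, and the model cannot use it.

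The piece-wise curve could then sit away from the power-law curves at Months 24-36 because of its covariance and not its shape. Long-term persistence up to three years is a stated purpose of the study, and the three curves are its model-based summary.

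**Working it through.** **1. The plan's own figures.** The 20% yearly rate reproduces the planned numbers: 1005 × 0.8 = 804 at Month 12, and 330 × 0.8² = 211.2, stated as 211, at Month 25. The Table 17 half-width at SD 0.40 is t(0.975, 803) × 0.40/√804 = 0.0277, stated as 0.028. The same rate leaves 330 × 0.8³ = 169 one-dose participants (51%) at Month 36. The documents give no figure for the persistence model.

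**2. What the code assumes.** Let σ_b, σ_s and σ_e be the intercept, slope and residual SDs, ρ the level-decay correlation, and u, v the months since Month 1.

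- Planned code: Cov(y_u, y_v) = σ_b², the same for every pair of visits.
- With a random slope: Cov(y_u, y_v) = σ_b² + ρσ_bσ_s(u + v) + σ_s²uv.

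Take assumed values σ_b = 0.30, σ_e = 0.12, σ_s = 0.008 log10 per month and ρ = 0.

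- With no slope variance, every pair correlates at 0.09/(0.09 + 0.0144) = 0.86.
- With it, Day 31 and Month 36 correlate at 0.09/(0.323 × 0.428) = 0.65, and Months 30 and 36 at (0.09 + 0.000064 × 29 × 35)/(0.398 × 0.428) = 0.91.

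The implied Month 36 SD is √(0.09 + 0.0144 + (35σ_s)²), or 0.37, 0.43 and 0.48 for σ_s = 0.005, 0.008 and 0.010. All lie inside the protocol's planning range of 0.30-0.50.

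**3. Month 36 bias, large samples.** Assumptions not in the documents: the SDs above, a piece-wise linear mean, 20% yearly loss, and dropout log-odds rising by 0.7-1.2 per SD of lower last observed titre. Ratio = 10^bias.

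| Level-decay correlation | Bias, planned model (log10) | GMT ratio |
|---|---|---|
| -0.5 (higher peaks decay faster) | -0.014 to -0.006 | 0.97 to 0.99 |
| -0.3 | -0.003 to +0.016 | 0.99 to 1.04 |
| 0 | +0.007 to +0.038 | 1.02 to 1.09 |
| +0.3 (higher peaks decay more slowly) | +0.022 to +0.066 | 1.05 to 1.16 |

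With a random slope the bias stayed within about 0.004 in every row (ratio 0.99-1.01).

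**4. A second set of assumptions at trial size.** Groups of 345/330/330, total SD 0.40 before slope variation, residual SD 0.20, breaks at Months 6 and 18, ρ = 0. Annual-group data stop at Month 12 and flexible-group data at Month 24.

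| Slope SD | Odds of loss per SD lower titre | Ratio, planned model | EMPIRICAL 95% coverage |
|---|---|---|---|
| 0.005 | ×2 | 1.02 | 92.5% |
| 0.005 | ×4 | 1.03 | 91.5% |
| 0.010 | ×2 | 1.08 | 74% |
| 0.010 | ×4 | 1.13 | 42.5% |

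- In the last two rows the mean EMPIRICAL standard error was 0.026 and 0.025, against a true SD of 0.027. The limits have about the right width and the wrong centre.
- Those two rows imply a Month 36 SD of about 0.53, just above the planning range.
- Loss unrelated to titre: ratio 0.997-1.002.
- Equal slopes: no bias, even with titre-related loss.
- High titres leaving more often (slope SD 0.010, odds ×0.5): ratio 0.93.
- With a random slope, the ratio in the main pooled scenarios was 0.995-1.003 and coverage 95%-99%. On the one-dose group alone it was about 0.99, with coverage of 92%-93%.

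**The case against.** The strongest reply is that the bias needs two things the documents do not supply: decay that differs between people, and loss that depends on titre. The protocol's 20% is a planning rate for non-evaluable participants. It is not a dropout forecast and says nothing about who is lost. The listed withdrawal reasons do not mention titre, and some per-protocol exclusions remove single visits only, unlike the permanent dropout simulated here. This stands. A reader might infer that the planned loss by itself distorts the curve. It does not.

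A reader might also infer that the model overstates late titres. That holds for zero or positive level-decay correlation with low titres leaving. A correlation of -0.5, or high titres leaving, reverses it. The SAP's own power-law code leaves that correlation free (the term ska).

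A third tempting inference is that the limits are falsely narrow. EMPIRICAL is specified, and the standard errors come out about right.

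Finally, the analysis is exploratory, all analyses are descriptive, and the GMT analyses at Months 24-36 do not use this code. Two models with individual decay are plotted alongside. This limits the consequence but does not explain why one of three compared models has the more restrictive covariance. The full-follow-up sensitivity analysis in section 5.4.3.4 is optional, tied to the pandemic, and does not address selective loss.

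**Conclusion.** The concern holds in conditional form. The piece-wise model assumes a common decay that the SAP's other two persistence models do not assume. If decay varies and loss depends on earlier titres, its late means are biased, and the EMPIRICAL limits will not reveal it.

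Under the assumptions in step 3, the Month 36 ratio lies between about 0.97 and 1.16. At the low end of the slope variation and with no correlation it is about 1.02, which is minor. The sign cannot be settled from the documents, and if either condition fails there is no bias. No primary or secondary endpoint analysis is affected. This is a cheap improvement to an exploratory model, not a threat to the trial's main results.

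**What to change.** In SAP section 5.4.3.3, change the piece-wise statement to `RANDOM intercept int_m / SUBJECT=pid TYPE=UN;`. Select the break points by AIC with that covariance in place. Fall back to intercept only if the fit fails, under the section's existing allowance for convergence problems, and report when this was done.

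The cost is one line, two more covariance parameters (slope variance and level-slope covariance) and a small risk of non-convergence. One limit should be stated: a slope linear in months does not fully match decay that varies on log time. Fitted to power-law-type data (SD of a 0.10), it left a ratio of 0.98-0.99. If the sponsor prefers intercept only, the SAP should say why a common decay is acceptable.
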